#### 7.8.1.1 Assignment of AEs to treatment

The analysis of adverse events will be based on the concept of treatment emergent adverse events. That means that all adverse events occurring between first drug intake till 7 days after last drug intake will be assigned to the randomised treatment. All adverse events occurring before first drug intake will be assigned to ‘pre-treatment’ and all adverse events occurring after last drug intake + 7 days will be assigned to ‘post-treatment’.

#### 7.8.1.2 Analysis of other significant AEs

Other significant AEs will be reported and summarised according to ICH E3 criterion [\[3\]](#). Thus, AEs classified as ‘other significant’ will include those non-serious and non-significant adverse events with:

- (i) ‘action taken = discontinuation’ or ‘action taken = reduced’, or
- (ii) Marked haematological and other lab abnormalities or lead to significant concomitant therapy as identified by the Clinical Monitor/Investigator at a Medical Quality Review meeting (MQRM) or BRPM.

#### 7.8.1.3 AE summaries

An overall summary of adverse events will be presented.

The frequency of patients with adverse events will be summarised by treatment, primary system organ class and preferred term. AEs will also be reported by intensity. Separate tables will be provided for patients with other significant adverse events, for patients with adverse events of special interest (AESI), for patients with serious adverse events, for patients with AEs leading to discontinuation, and for patients with drug-related AEs.

The system organ classes will be sorted according to the standard sort order specified by EMA, preferred terms will be sorted by frequency (within system organ class).

The following AE summaries will also be provided at week 16, including data up to visit 10 date only: AE overall summary, the frequency of patients with AEs summarised by treatment, primary system organ class and preferred term, frequency of patients with AEs reported by intensity, patients with other significant adverse events, patients with adverse events of special interest (AESI), patients with serious adverse events, patients with AEs leading to

discontinuation, patients with drug-related AEs, and analyses of hypoglycaemic events (as described in [Section 7.8.1.4](#)).

#### 7.8.1.4 Analysis of hypoglycaemic events

The investigator will record for each AE whether it represents a hypoglycaemic event and, if so, record additional information to assess the intensity of the hypoglycaemic event. On the basis of this information the hypoglycaemic event will be classified as:

- asymptomatic hypoglycaemia: event not accompanied by typical symptoms of hypoglycaemia but with a measured plasma glucose concentration  $\leq 3.9$  mmol/L (70 mg/dL),
- documented symptomatic hypoglycaemia with a measured plasma glucose concentration  $\geq 3.0$  mmol/L and  $\leq 3.9$  mmol/L ( $\geq 54$  mg/dL and  $\leq 70$  mg/dL): event accompanied by typical symptoms of hypoglycaemia,
- documented symptomatic hypoglycaemia with a measured plasma glucose concentration  $< 3.0$  mmol/L ( $< 54$  mg/dL): event accompanied by typical symptoms of hypoglycaemia but no need for external assistance,
- severe hypoglycaemic episode: event requiring the assistance of another person to actively administer carbohydrate, glucagon or other resuscitative actions.
- symptomatic hypoglycaemia and plasma glucose concentration  $> 3.9$  mmol/L (70 mg/dL)
- symptomatic hypoglycaemia and plasma glucose concentration not measured

Different tables will be shown for (i) patients with investigator defined asymptomatic or symptomatic hypoglycaemia reported as AE or non-AE, and (ii) patients with confirmed hypoglycaemic adverse events, i.e. hypoglycaemic adverse events that had a plasma glucose concentration  $\leq 70$  mg/dL or required assistance.

The number of patients with hypoglycaemia according to investigator's judgement will be tabulated by treatment group. A subgroup analysis of confirmed events with respect to age category, rescue therapy and renal function will be performed and the impact of treatment on the occurrence of hypoglycaemia will be explored using logistic regression with model involving treatment and continuous baseline HbA1c. Time to the onset of the first hypoglycaemia will be analysed by Kaplan-Meier estimates. The logistic regression and Kaplan-Meier analysis will be performed on confirmed events.

Summaries of hypoglycaemic events will include total number of hypoglycaemic events, descriptive hypoglycaemic event rate, number of episodes per patient, severity and intensity of the worst episode, action taken, minimum glucose level of worst episode, and time to onset of first episode. Hypoglycaemic events will also be summarised by baseline eGFR category (CKD staging), background medication and age group.

In the number of episodes analysis, hypoglycaemic events will be collapsed with the collapsing following the description at the start of [Section 7.8.1](#) but the condensing will not be conducted in order to maintain multiple episodes per patient.

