7.3.4 Safety analyses

Standard safety analyses will be performed on the TS.

Safety analyses will be descriptive in nature and will be based on BI standards. No formal inferential analysis is planned.

Adverse events will be coded using the Medical Dictionary for Regulatory Activities (MedDRA). AEs occurring one day before the first intake of the double-blind treatment will be assigned to the 'screening period'. AEs occurring between the first intake of the double-blind treatment and seven days after the last intake of double-blind treatment will be assigned to 'double-blind treatment period' for evaluation. AEs occurring thereafter will be assigned to 'post-treatment period'.

Frequency of patients with AEs will be summarised by system organ class (SOC) and preferred term (PT). In addition, AEs by intensity, drug-related AEs, serious AEs, AESIs and hypoglycaemic events will also be summarised.

Descriptive statistics of laboratory values for the change from baseline will be provided. Frequency tables of changes with respect to the reference range between baseline and last value on treatment will also be presented.

Change from baseline will be summarised for vital signs.

Further details on the safety analysis will be specified in the TSAP.

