7.6 RANDOMISATION

The trial will be performed as a double-blind design with respect to placebo and 2 active treatment groups of empagliflozin (10 mg and 25 mg). Patients who meet the inclusion criteria but not meet the exclusion criteria will be randomised in 1:1:1 ratio to each treatment group at Visit 5.

The randomisation will be stratified by the following factors:

- Baseline HbA_{1c} (at Visit 1 for insulin alone, Visit 4 for insulin with one OAD) (<8.5% or <69.4 mmol/mol, ≥8.5% or ≥69.4 mmol/mol)
- Baseline Renal function (at Visit 4) (eGFR <60 mL/min/1.73 m², eGFR ≥60 mL/min/1.73 m²)
- Type of insulin therapies (basal insulin therapy, other insulin therapy)

The randomisation of patients to the treatment groups will be performed via an IRT. BI will arrange for the randomisation as well as packaging and labelling of trial medication. The randomisation list will be generated using a validated system, which involves a pseudorandom number generator and a supplied seed number so that the resulting allocation of medication numbers to treatment is both reproducible and non-predictable. The access to the randomisation codes will be controlled and documented.

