#### **7.4.1 Primary efficacy analysis**

The primary analysis is an analysis of covariance (ANCOVA) comparing the change from baseline in HbA1c after 16 weeks of treatment. All randomised treatment groups will be included in the same analysis. The statistical model will be:

Change from baseline in HbA1c after 16 weeks = overall mean + baseline HbA1c + treatment + baseline renal function + type of insulin therapies + random error

This model includes effects accounting for the following sources of variation: 'baseline HbA1c', 'baseline renal function', 'type of insulin therapies' and 'treatment'. 'Treatment', 'baseline renal function', and 'type of insulin therapies' are fixed classification effects and 'baseline HbA1c' is a linear covariate. Note that baseline renal function refers to the eGFR categorization ( $\geq 60$  mL/min/1.73 m^2,  $< 60$  mL/min/1.73 m^2). Such categorization is applicable to the analysis of other endpoints as well.

The random error is assumed to be normally distributed with mean 0 and unknown variance. The primary analysis will be performed on the FAS with treatment assignment as randomised.

A hierarchical testing sequence will be used as defined in the protocol.

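### The exploratory logistic model for hypoglycaemia leaves out two of the three stratification factors, insulin type and renal function; adding them is a cheap, modest improvement

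*SAP*

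**What the plan says.** Protocol 7.6 stratifies the 1:1:1 randomisation by three factors: baseline HbA1c, renal function (eGFR below 60 v 60 mL/min/1.73 m² or above) and insulin regimen, the last listed as "Type of insulin therapies (basal insulin therapy, other insulin therapy".

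The primary ANCOVA takes account of all three. HbA1c is a linear covariate, and SAP 7.4.1 states that "baseline renal function', and 'type of insulin therapies' are fixed classification effects". The MMRM for lipids and FFA in SAP 7.8.6 also carries baseline eGFR and insulin type.

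For hypoglycaemia, SAP 7.8.1.4 says that "the impact of treatment on the occurrence of hypoglycaemia will be explored using logistic regression with model involving treatment and continuous baseline" HbA1c, and adds: "The logistic regression and Kaplan-Meier analysis will be performed on confirmed events". Insulin type and renal function are not in the model, and no reason is given. The same section plans tables: "Hypoglycaemic events will also be summarised by baseline eGFR category (CKD staging), background medication and age group". SAP 7.8.1.3 repeats the hypoglycaemia analyses with data up to Visit 10. On safety analyses as a whole, Protocol 7.3.4 states: "No formal inferential analysis is planned".

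**The concern.** Protocol 2.3 recognises that hypoglycaemia risk may rise when empagliflozin is added to insulin. The trial admits basal, bolus, premix and basal-bolus regimens, and the sponsor considered basal v other important enough to stratify on. If these groups start from different hypoglycaemia risks, leaving regimen out of a logistic model has two consequences:

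- The fitted treatment odds ratio is nearer 1 than the odds ratio within a regimen.
- The model-based standard error treats the arms as if regimen could differ by chance, although stratification has balanced it. The test is therefore somewhat conservative.

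Both make added hypoglycaemia a little harder to see, which is the unhelpful direction for a safety question. The same applies to the Visit 10 repeat.

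**Working it through.** **Inputs.** The plan states no figure for the hypoglycaemia model. From the documents come the model terms, the strata and 89 patients per arm (Protocol 7.7). That arm size reproduces: a difference of 0.5 with SD 1.0 gives t-test power 0.8999 at 85 and 0.9032 at 86 per arm, and 86/0.97 = 88.7, so 89. Hypoglycaemia risks, the regimen split and the treatment effect are not in the documents. The values below are assumptions.

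**Assumed cases.** The within-regimen treatment odds ratio is 2.0. Placebo risks for basal v other, with the share on other insulin, are: A 15% v 45%, 60%; B 10% v 50%, 60%; C 15% v 35%, 50%. The implied regimen odds ratios are:
- A: (0.45/0.55)/(0.15/0.85) = 4.6
- B: (0.50/0.50)/(0.10/0.90) = 9.0
- C: (0.35/0.65)/(0.15/0.85) = 3.1

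**Step 1, odds ratio without regimen (case B).**
- Placebo risk: 0.4×0.10 + 0.6×0.50 = 0.340.
- Doubling the odds gives treated risks of 0.1818 (basal) and 0.6667 (other). Mixed: 0.4×0.1818 + 0.6×0.6667 = 0.4727.
- Odds ratio: (0.4727/0.5273)/(0.340/0.660) = 1.74.

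**Step 2, standard errors of the log odds ratio (case B; baseline HbA1c set aside).**
- Planned model, 1/(n·p·q) summed over the two arms: 1/(89×0.34×0.66) + 1/(89×0.4727×0.5273) = 0.0951, so SE 0.308.
- With regimen added: 35.6 basal and 53.4 other patients per arm. The within-regimen variances are 0.5009 and 0.1592. Combined: 1/(1/0.5009 + 1/0.1592) = 0.1208, so SE 0.348.
- Actual sampling SD of the planned estimate when regimen is balanced, Σw·p·q/[n(pq)²] summed over arms: 0.186/(89×0.2244²) + 0.1928/(89×0.2493²) = 0.0415 + 0.0349 = 0.0764, so SD 0.276.

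**Step 3, all cases.** z is the log odds ratio divided by its model SE. The last column is from 4,000 simulated trials per case, with 89 per arm, insulin type balanced and baseline HbA1c in both models.

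| Case | Regimen OR | OR without regimen | Planned SE | Actual SD of planned estimate | Adjusted SE | z planned → adjusted | 95% CI excludes 1, planned → adjusted |
|---|---|---|---|---|---|---|---|
| A | 4.6 | 1.85 | 0.310 | 0.292 | 0.330 | 1.99 → 2.10 | 51.8% → 56.0% |
| B | 9.0 | 1.74 | 0.308 | 0.276 | 0.348 | 1.80 → 1.99 | 43.4% → 52.0% |
| C | 3.1 | 1.92 | 0.327 | 0.317 | 0.339 | 1.99 → 2.05 | 50.4% → 53.6% |

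The gains are 4.2, 8.6 and 3.2 percentage points. They arise because the log odds ratio grows by more than its standard error does.

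**Step 4, no treatment effect.** The mixed risks are equal in both arms, so the odds ratio is 1 either way. Simulated rejection, planned v adjusted, is 3.6% v 4.9% (A), 3.1% v 5.0% (B) and 4.4% v 5.0% (C). Reported SE against actual SD for the planned model is 0.323 v 0.307, 0.321 v 0.295 and 0.353 v 0.351.

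**Step 5, weaker regimen effects.** Over a grid with regimen odds ratios of 1.5 to 5 and placebo rates of 10% to 50%, an odds ratio of 2.0 appears as 1.99 down to 1.81. At a regimen odds ratio of 1.5, a 30% placebo rate and half the patients on other insulin, z moves only from 2.185 to 2.194.

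**The case against.** The strongest reply is that nothing is wrong in a strict sense. Randomisation balances regimen, so the planned odds ratio is not confounded. It is an odds ratio averaged over regimens rather than conditional on them, and both are legitimate targets. A reader might infer from the shift between 2.0 and 1.74–1.92 that the planned estimate is biased. The documents do not support that, because the shift is a property of the odds ratio.

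A reader might also infer that the planned confidence interval is too wide and that adding the factors would narrow it. That carries over a result for linear models. In logistic regression the prognostic term raises the standard error. The ratio of upper to lower 95% limit goes from 3.37 to 3.65 (A), 3.35 to 3.91 (B) and 3.61 to 3.77 (C). What remains is the narrower statement that the planned standard error exceeds the actual sampling SD of its own estimate under stratified allocation, by very little when regimen predicts weakly.

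The analysis is also exploratory, safety has no formal inference, and the plan adds tables by background medication and eGFR category, a subgroup analysis by renal function, and Kaplan-Meier estimates. A signal would not rest on this one odds ratio. This lowers the severity. It does not remove the point, because the tables give no adjusted treatment effect.

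Finally, nothing in the documents shows how strongly regimen predicts hypoglycaemia, and cases A and B assume a strong effect. That objection stands, so the sizes are illustrations.

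**Conclusion.** The omission is plain in the text and out of line with the SAP's own primary and lipid/FFA models. Its consequence is modest and conditional. If regimen odds ratios are about 3 to 9, a within-regimen odds ratio of 2.0 is reported as about 1.92 to 1.74, and the chance that the 95% CI excludes 1 is about 3 to 9 percentage points lower than with adjustment. If regimen matters little, the loss is close to nil. No conclusion on efficacy depends on this model. It is a low-severity improvement.

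**What to change.** In SAP 7.8.1.4, specify the logistic model as treatment + continuous baseline HbA1c + type of insulin therapies (basal, other) + baseline renal function (<60, ≥60 mL/min/1.73 m²). Name the two renal levels explicitly, because SAP 7.4 refers to CKD staging while 7.4.1 uses the two-level split. The Visit 10 repeat under SAP 7.8.1.3 follows automatically.

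Add a sparse-data rule: if confirmed events or patients in the <60 stratum are few, keep insulin type and drop renal function. That stratum may be small, since Protocol 3.3.3 excludes patients with eGFR below 45 at screening or run-in.

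The cost is about two lines of SAP text and no new data, as both variables are already used in the primary model. The downside is a somewhat wider interval for the log odds ratio, and possible instability if events are few. The report should describe the result as conditional on regimen and renal function.

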2.3 BENEFIT - RISK ASSESSMENT

The currently-known safety profile of empagliflozin is outlined in the latest IB [[c01838761](#)].

According to the drug assignment planned in this trial, 2/3 (66.6%) of the patients with T2DM participating in this trial may derive a direct benefit from being treated with an additional active compound and not a placebo. The patients will receive an investigational medication empagliflozin that has already demonstrated favorable HbA_{1c} and glucose changes at the tested doses. One third (33.3%) of patients will receive placebo and these patients thus have a higher probability of treatment failure, i.e., of increase in FPG and HbA_{1c}. However, appropriate inclusion/exclusion criteria of HbA_{1c} and FPG value and

Proprietary confidential information © 2016 Boehringer Ingelheim International GmbH or one or more of its affiliated companies

criteria for rescue therapy and patient discontinuation will ensure an adequate treatment in case of any clinical concern.

Because of the mechanism of action of empagliflozin, the risk of hypoglycaemic episodes is considered to be low. However, with empagliflozin in combination with insulin, the risk of hypoglycemia may be increased compared to the treatment with insulin alone. Symptoms attributed to hypoglycemia will be closely monitored in the trial.

In addition, although, diabetic ketoacidosis (DKA) has not been observed in clinical trials of empagliflozin in Type 2 DM patients so far in Japan, special attention will be paid to prevent DKA according to the recommendation from “Committee on the proper use of SGLT2 inhibitors” of the Japanese Diabetes Society that requests physicians to pay attention to DKA when using an SGLT2 inhibitor [[R15-2908](#)].

Rare cases of DKA have been reported in patients treated with SGLT2 inhibitors, including empagliflozin. In a number of reported cases, the presentation of the condition was atypical with only moderately increased blood glucose values, below 14 mmol/L (250 mg/dL).

The risk of DKA must be considered in the event of non-specific symptoms such as nausea, vomiting, anorexia, abdominal pain, excessive thirst, difficulty breathing, confusion, unusual fatigue or sleepiness. In addition it needs to be taken into account that, due to the insulin independent mode of action, there is a possibility that ketoacidosis in patients treated with SGLT2 inhibitors is not accompanied by typical hyperglycemia as usually expected for DKA.

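### Hypoglycaemia: recurrent episodes and the event rate are summarised descriptively, but the only modelled comparison between arms is a yes/no logistic regression without follow-up time

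*SAP*

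**What the plan says.** Protocol section 2.3 identifies the risk: "with empagliflozin in combination with insulin, the risk of hypoglycemia may be increased" relative to insulin alone. Protocol section 7.3.4 makes the safety analyses descriptive: "No formal inferential analysis is planned".

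SAP section 7.8.1.4 then sets out three layers of analysis.

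- One regression: "the impact of treatment on the occurrence of hypoglycaemia will be explored using logistic regression with model involving treatment and continuous baseline" HbA1c. No follow-up time enters the model.
- Time to first event: "Time to the onset of the first hypoglycaemia will be analysed by Kaplan-Meier estimates". No log-rank test, Cox model or effect estimate is named. For both of these layers, "The logistic regression and Kaplan-Meier analysis will be performed on confirmed events".
- Descriptive tables: "Summaries of hypoglycaemic events will include total number of hypoglycaemic events, descriptive hypoglycaemic event rate, number of episodes per patient", together with severity, action taken and time to first episode. For the episode count, "the condensing will not be conducted in order to maintain multiple episodes per patient".

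Confirmed events are hypoglycaemic adverse events with plasma glucose of 70 mg/dL or below, or with a need for assistance. SAP section 7.8.1.3 repeats the hypoglycaemia analyses on data up to the Visit 10 date. Neither document gives an expected hypoglycaemia rate or its spread between patients.

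**The concern.** Insulin-treated patients who are asked to measure glucose at least daily for 52 weeks can have several episodes each. The protocol itself responds to repetition: repeated symptomatic hypoglycaemia is a ground for changing insulin (section 4.2.1), and repeated episodes that cannot be managed are a ground for withdrawal (section 3.3.4.1). The logistic model cannot tell one episode from ten, and it treats a patient followed for 8 weeks like one followed for 52.

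Two things follow. If many patients have at least one event, the yes/no outcome leaves little room to show a difference in frequency. If follow-up differs between arms, the odds ratio mixes frequency with time at risk. The plan keeps the data that would address both, but attaches no between-arm estimate or interval to the rate.

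**Working it through.** **The plan's own sample size.** Protocol section 7.7 gives 86 analysed and 89 randomised per arm for HbA1c (difference 0.5, SD 1.0, two-sided 5%, 90% power). The normal approximation gives 2 × (1.960 + 1.282)² × 1.0² / 0.5² = 84.1, so 85. With the noncentral t distribution, 85 gives 89.99% and 86 gives 90.3%. Then 86 / 0.97 = 88.7, so 89. The figures reproduce, but they were not chosen for hypoglycaemia.

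**Inputs for the comparison.** From the documents: 89 per arm and 20% loss over 52 weeks. Assumed, because the documents are silent: true rate ratio 1.5, placebo rate m₀ of 0.2 to 10 episodes per patient-year, and dispersion k of 0 to 8 (variance = mean + k × mean²).

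**Formulas**, with equal follow-up of one year and no covariate:

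- Rate model: var(log rate ratio) = [(1/m₀ + k) + (1/m₁ + k)] / n
- Yes/no model: p = 1 − (1 + k·m)^(−1/k), or 1 − e^(−m) when k = 0; var(log odds ratio) = 1/[n·p₀(1−p₀)] + 1/[n·p₁(1−p₁)]
- Information kept = (z of the yes/no model / z of the rate model)²

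**Worked case, m₀ = 1, k = 1, n = 89.**

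- Rate model: variance (2 + 1.667)/89 = 0.0412, z = 0.405/0.203 = 2.00, power 51.5%.
- Yes/no model: p₀ = 0.50, p₁ = 0.60, log odds ratio 0.405, variance 0.0449 + 0.0468 = 0.0918, z = 0.405/0.303 = 1.34, power 26.7%.
- Information kept: (1.34/2.00)² = 0.45.

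**Range over k = 0 to 8:**

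| Placebo rate per patient-year | Information kept by yes/no model | Lost |
|---|---|---|
| 0.2 | 57-89% | 11-43% |
| 0.5 | 42-73% | 27-58% |
| 1 | 33-50% | 50-67% |
| 2 | 20-29% | 71-80% |
| 5 | 1-19% | 81-99% |

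At 10 per year the yes/no model keeps 0-16%.

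**Simulation with 20% exponential dropout**, the same in each arm (400 runs per case, 89 per arm, rate ratio 1.5): logistic without follow-up time against negative binomial with exposure offset.

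| Rate, k | Logistic power | Negative binomial power |
|---|---|---|
| 0.5, 1 | 25% | 41% |
| 0.5, 4 | 12% | 19% |
| 2, 1 | 21% | 52% |
| 2, 4 | 12% | 25% |
| 5, 1 | 16% | 72% |

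With no true difference, rejection rates were 4.2-6.0% for logistic and 3.5-5.8% for the rate model, so the gain is not bought with false positives in these cases.

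**The Visit 10 period.** What drives the loss is the expected count over the period analysed. Sixteen weeks is 16/52 = 0.31 year, so 2 episodes per year becomes about 0.62 per patient and falls between the 0.5 and 1 rows. The gain is therefore smaller up to Visit 10 than over 52 weeks.

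**The case against.** A reader might infer that hypoglycaemia is compared only as yes/no, that recurrences and exposure are thrown away, and that most of the information is lost. The SAP does not support the first two. The Kaplan-Meier estimates use follow-up time, and the same section tabulates "total number of hypoglycaemic events, descriptive hypoglycaemic event rate, number of episodes per patient" and switches off condensing to keep repeats. The third holds only at about 1 episode per patient-year or more, or near 0.5 with heavy overdispersion. The modelled endpoint also points away from very high rates: it is limited to adverse events, and protocol section 5.3.3 requires adverse event reporting only for values below 54 mg/dL and for symptomatic or severe episodes. Asymptomatic readings from 54 to 70 mg/dL need not count.

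Further, safety analysis is descriptive by protocol and the trial was not sized for hypoglycaemia, so power is only a measure of precision here. Even the rate model has about 50% power in the worked case. This stands, and it limits how serious the point is. But the SAP has already chosen to model hypoglycaemia, and a rate ratio with an interval is estimation that fits an exploratory analysis.

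The strongest technical objection is that later episodes depend on earlier ones. Repeated symptomatic or severe episodes permit an insulin change even before Visit 10, insulin is adjustable at discretion afterwards, and unmanageable hypoglycaemia leads to withdrawal. First-event measures are less exposed to this, and the calculations above generate clean negative binomial data, which favours the rate model. This is a real limitation of a 52-week rate ratio. It is a reason to lead with the Visit 10 period and keep the first-event analyses.

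**Conclusion.** The point holds as a modest improvement in precision; it does not show an error in the plan. The single modelled comparison between arms ignores repeat episodes and time at risk, while the rate that uses both is left without a ratio or interval. The size of the loss rests on assumed rates, dispersion and a rate ratio of 1.5: from 11-43% at 0.2 episodes per patient-year to over 70% at 2 or more. The rate model was more precise in every case tested with a rate ratio of 1.5, but the documents cannot show where in that range the trial will fall. Nor do they show that follow-up will differ between arms, so bias in the odds ratio is a possibility rather than a finding.

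**What to change.** Add to SAP section 7.8.1.4 an exploratory negative binomial regression of the number of collapsed confirmed episodes per patient, with log(time at risk) as offset and treatment and baseline HbA1c as terms. Report rate ratios with 95% confidence intervals for 10 mg and 25 mg against placebo, first up to Visit 10, when the insulin dose is restricted, and then over the whole treatment period. Define time at risk to match the existing rules: first intake to 7 days after last intake, cut at the Visit 10 date for the first analysis. State that the count uses confirmed events, since the sentence on the descriptive summaries does not say so. Keep the logistic and Kaplan-Meier analyses.

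The cost is a paragraph of SAP text and one extra model; the collapsing rule and episode counts are already planned. The downsides are a distributional assumption and a caveat, to be printed with the 52-week ratio, that insulin changes and withdrawals can follow earlier episodes.
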